The most frequently cited danger signs of heart failure (HF) are new onset or worsening of fatigue, dyspnea and edema. In previous research, patients did not recognize worsening HF, due to 3 primary reasons: (1) danger signs were non-specific and misinterpreted as stress, an external force or another comorbidity, (2) danger signs were unrecognized due to the subtle nature of worsening status, or (3) when patients eliminated or minimized activities that prompted danger signs, they interpreted the results as improvement in status. Lack of recognition of HF danger signs and lack of understanding of how to control and minimize danger signs could lead to their escalation and prompt all-cause and HF-related health care resource utilization (HCRU: emergency department care, hospitalization, death/ventricular assist device/cardiac transplantation referral or placement, or an unscheduled/urgent office visit). During hospitalization, patient education is delivered, but it is assumed that patients understand the danger signs and simply need education in self-care behavior expectations. We hypothesize that patients must understand HF danger signs to have self-confidence in recognizing them and in taking steps to minimize or eliminate their occurrence post hospital discharge. Therefore, the purposes of this randomized, controlled trial are to determine if video education in HF danger signs recognition and control prior to discharge and post-discharge reduces all-cause and HF-related 30-, 60-, 90- and 180-day HCRU. Research nurses will deliver the intervention during hospitalization, and patients and family members will receive a link to a website and a DVD of content to review videos as often as desired post-discharge. The primary end-point is 30-day HF-related HCRU. A total of 732 patients (658 + 10% attrition) with decompensated HF will be enrolled. Patients will be followed by telephone or medical record review to determine HCRU post index hospitalization.

INTRODUCTION

Chronic heart failure (HF) is a costly diagnosis;¹ especially for patients who are hospitalized due to decompensation. Heart failure decompensation and hospitalization place patients at high risk for rehospitalization, exacerbating costs of care and potential penalties associated with the Patient Portability Affordable Care Act.²

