Hypothesis 3c: Repeat viewing of videos by patients, compared to 1-time viewing in-hospital and/or viewing of videos by family supporters/caregivers in hospital and/or post discharge, compared to viewing only by patients, will be associated with *higher self-efficacy for HF self-care actions* (due to symbolic modeling of self-care actions)

METHODS

Design: The study will use a 2-group, randomized, placebo-controlled, single blinded, design. Healthcare providers and unit nurses will be blinded to group assignment, but may learn about HF danger signs education if they enter the patients' room during intervention delivery or discuss the intervention prior to hospital discharge.

In brief, the research intervention involves 3 novel short videos (fatigue, dyspnea and edema) that will be viewed back-to-back by intervention group patients using a DVD player. Wellflix, Inc. videos are research-informed, use behavioral-modeling, are personally-tailored and are available 24/7 online. Patients will receive a handout sheet with the web address to view the videos after discharge and will be encouraged to view them with family members.

Sample (including sample size calculation) and Setting

A total of 732 patients will be enrolled (366 per group) and consist of adults with chronic HF (diagnosis \geq 2 months) who are hospitalized for acute decompensated HF within Cleveland Clinic Hospitals. This sample size includes a 10% attrition rate. Sample size was based on power calculations using 30-day first occurrence of HF-related HCRU (hospitalization, emergency department visit, mortality, cardiac transplantation or VAD). The current expected 30-day HF-related readmission rate is 20% among the control group. Allowing for other HCRU components, a control group HCRU rate of 28% is expected at 30 days. At 90 days, HCRU rate of 46% is expected in the control group. Sample size calculations were performed using SAS software (version 9.4; Cary, NC) and assume use of two-sided Pearson -chi square tests. With 329 patients in each group there will be 80% power to detect a 33% relative decrease (9.2% absolute decrease) in first occurrence of HF-related HCRU from a HCRU rate of 28% in the control group. With this sample size there would also be 85% power to detect a relative decrease of 25% (absolute decrease of 11.5%) from a control group event rate of 46% at 90-days. Allowing for 10% loss to follow-up, we will enroll 366 patients per group (732 total).

NCT-03657459

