The fatigue and dyspnea video's will be viewed back-to-back and the edema video will be added for patients with a history of edema. There are 4 versions of each video: (1) based on race (Caucasian and African-American) and sex (male and female)—to promote symbolic modeling— by patients who look like video models (as stated in the introduction). Scripts for each video were developed jointly by [name], Director of Media and Education for Wellflix, Inc. and [name] PhD, principal investigator and clinical nurse specialist in HF. Content includes recognition and assessment of fatigue, dyspnea and edema and specific actions to take to reduce the danger signs or prevent worsening (dietary sodium and/or fluid restriction, physical activity/exercise and contacting the doctor).

Overall video viewing time for all 3 videos is 9:50 minutes; the fatigue and dyspnea videos that all intervention patients will view are 6:50 minutes:

- *Fatigue* is 2:20 minutes + end text list= 3:00 minutes;

NCT-03657459

- *Dyspnea* is 1:40 minutes + dyspnea “yes” or “no” management (2 options; patient selects the option that matches current status) = 3.50 minutes
- *Edema* is 2:40 minutes + end text list= 3:00 minutes;

During hospitalization, videos will be loaded into an iPAD and will be viewed through the iPAD.

Patients have an opportunity to view videos post-discharge as desired and able. *Post discharge*, videos can be in 2 ways: (1) via the Wellflix, Inc. site at www.wellflix.net/DangerSignsCC or (2) by DVD player (DVD created by Wellflix, Inc for this research), for patients who have DVD player capability and prefer this method.

NOTE, at/after 180-day follow up data are collected, *usual care group* patients will be offered access to Wellflix, Inc. videos used in this research study via mailing of a handout sheet developed specifically for them (that contains the web address and a note of encouragement to view the videos.

Outcomes and Measurement

HCRU. Includes all-cause and HF-related hospitalization, ED visit, death, cardiac transplantation, or VAD placement at 30-, 90-, and 180-days \pm 6 days in both groups. Data will be retrieved from medical records when available or via telephone call to patients.

- Patients will receive a calendar to keep track of HCRU events in-between phone calls.
- Research nurses will use a case report form to record HCRU events

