Patient characteristics and medical history at baseline. Standard patient characteristics that are used in many research studies of patients with HF, will be used in this research as they span themes of interest and provide global information about participants. Items include height and weight, highest education, comfort living on current household income, current signs and symptoms of HF, comorbid conditions and billing data retrieved from Cleveland Clinic billing database (age, race, gender, marital status, discharge disposition, and length of hospital stay). The *Charlson Comorbidity Index* will be used to collect medical comorbidity history. This index was developed to classify comorbid conditions which might change the risk of mortality.²⁴⁻²⁹ The score will be categorized into 3 groups (score of 1-2 = 1; 3-4 = 3; 5 or more = 5). In one study with 33,940 patients with ischemic heart disease, the grouping demonstrated a strong relationship with mortality rate.²⁹ In 2011, the tool was reduced from 19 items to 12 items and each item was re-scored based on morbidity and mortality of medical conditions in the current era of medical therapies.³⁰ This data will also be used to describe the sample groups for similarity in acuity.

Video Watching Experiences in-hospital and at 30 day follow-up (intervention group only). A 3-item, investigator-developed survey will assess video watching characteristics: total number of watching’s, caregiver/family member video watching *in the hospital*, and

NCT-03657459

caregiver/family member video watching *in the post discharge* period, up to 30 days. Items use choose-the-best-response options.

Data Collection

Medical records will be assessed for inclusion and exclusion criteria before approaching patients. Research personnel will explain the study in a patient's room (in non-private rooms, a curtain will be drawn to separate beds and enhance confidentiality). After received verbal informed consent, patients will complete baseline data that includes assessment of functional status, dyspnea, fatigue and self-efficacy for managing symptoms immediately before hospitalization. Administration of the functional status, dyspnea and fatigue questionnaires will be randomly changed for each participant to allow for counterbalancing, since there item themes may have overlap/be similar. Baseline data collection should take 10 minutes or less.

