After completing baseline paperwork, patients will be randomly assigned to the usual care or usual care plus HF danger signs video education group using block randomization; with blocks of 20, to decrease the influence of external factors that could alter outcomes. The randomization assignment will be made by a QHS statistician.

After randomization to groups:

- Intervention group patients will receive usual hospital care and also, HF danger signs education via iPad by research personnel. Danger signs education can be administered at the time of enrollment. There is no need to wait until day of discharge, since HF danger sign messages are not individualized and discharge is a very busy time. Immediately prior to discharge, patients' focus may be on preparing to leave the hospital and not on education about HF, especially if patients believe that they have accurate perceptions of HF danger signals, even though in previous research, most subjects did not.
- Usual care group patients will be educated by their healthcare providers (including nurse/other caregivers). Education may include Elsevier HF videos that are shown on Cleveland Clinic hospital televisions.

A research nurse will use telephone calls or mailing methodologies to have the following 4/5 tools (40/43 items in total for usual care and intervention groups, respectively) completed at 30 ± 6 days: functional status, dyspnea, fatigue, self-efficacy for managing symptom and video watching experiences. Administration of functional status, dyspnea, and fatigue questionnaires will be randomly ordered (counterbalanced). The intervention-only group survey on video watching experiences will be administered last. It is expected that data collection will take ~ 10 minutes or less.

A research nurse will review EMRs of enrolled patients after the index (baseline) hospital discharge and at 30-, 60-, 90- and 180-days (± 6 days) for HCRU events.

- If not found in the EMR, telephone calls will be made to gather data.
- At baseline, research nurses will obtain home telephone number and the telephone number of a close relative or friend that can provide patient contact information, as needed.

NCT-03657459

Analyses

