The HF danger signs videos provide information that patients should understand, but that may not have been explicitly explained previously; therefore, it may be considered an extension of usual care education. Ideally, no new information is presented; as patients receive content about HF signs and symptoms and HF self-care actions via CC video education (in-hospital, when attentive) and via the HF handbook, which is sent home and can be re-given in ambulatory care. Danger signs video content was based on symbolic modeling; and has a *repeatable format*, if patients in the intervention group choose to utilize the on-line 24/7 viewing option post discharge. Patients do not need to be able to read and if they are forgetful or have mild memory impairment that was not documented at enrollment, they can replay videos multiple times.

Research personnel from the Office of Nursing Research and Innovation will recruit subjects, apply the intervention and collect data (at all sites). The main campus has multiple research projects in place, led by physicians, myself and other RNs. Research team personnel are accustomed to working with cardiology research nurses, as needed, to ensure patients are not approached for more than 1 research study.

Instruments that will be completed at baseline may be self- or research nurse-administered (patient demographics, HF characteristics, danger signs [dyspnea and fatigue], functional status and self-efficacy for managing symptoms). The patient demographics and HF characteristics instruments have been used many times in previous HF research and are short, simple and quick

NCT-03657459

to complete. Patients may become fatigued when completing baseline data collection forms; however, all 6 tools have only 71 items (in total) and all tools are short (12 or less items; each one should take about 3 minutes to complete).

- At baseline, all 6 tools should take and take under 20 minutes to complete. In previous research, patients were NOT burdened by data collection that included similar length instruments.
- At follow-up, telephone calls are only made when HCRU data is not available in medical records at 60-, 90- and 180-days. Data obtained from electronic medical records is consistently present, minimizing the occurrence of missing data.

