One data collection form will use a research number and CCF medical record number; as it will also contain names and phone numbers; however, all other baseline and follow-up data collection forms contain only research numbers. Only the research number will be recorded in the electronic database. Paper forms will be kept in a locked cabinet, in a locked office of the principal investigator and will be destroyed upon assurance that data in the electronic database is high quality, after enrollment is completed. Electronic data for analysis will use a research number; no patient identifiers will be used. All study results will be reported in aggregate.

NCT-03657459

SPSS will be the electronic database used to capture paper data. The electronic database will be maintained for 6 years after study completion. Paper documents will be destroyed once the initial analysis is complete.

This research project will be registered in www.clinicaltrials.gov.

References

4. van der Wal MH, van Veldhuisen DJ, Veeger NJ, Rutten FH, Jaarsma T. Compliance with non-pharmacological recommendations and outcome in heart failure patients. *Eur Heart J*. 2010;31:1486-93.

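### The trial is labelled placebo-controlled and single blinded, but the control is usual care and nobody masked to arm is named to decide which events are HF-related for the primary endpoint.

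*Combined protocol and SAP*

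**What the plan says.** **Label and masking.** The Design section states "The study will use a 2-group, randomized, placebo-controlled, single blinded, design". It then limits the masking: "Healthcare providers and unit nurses will be blinded to group assignment", and concedes that these staff may find out about the videos before discharge.

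**Control.** Data Collection describes the comparator: "Usual care group patients will be educated by their healthcare providers (including nurse/other caregivers". This may include the hospital's standard HF videos on television. No placebo or sham video is described.

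**Who treats and who collects.** The opening summary says "Research nurses will deliver the intervention during hospitalization". Under Feasibility, research personnel of one office "will recruit subjects, apply the intervention and collect data (at all sites".

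**Who finds and records events.** Data Collection has a research nurse review the EMR at each follow-up point and telephone when the information is not there. Outcomes and Measurement adds "Research nurses will use a case report form to record HCRU events". At 30 days the intervention group alone also completes a three-item video survey.

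**Endpoint.** The primary outcome is first HF-related hospitalization, ED visit, death, or transplantation/VAD at 30 days. The plan gives no operational definition of HF-related, no adjudication process and no masked assessor. The same composite for all causes is a secondary outcome at 30, 90 and 180 days.

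**The concern.** Two things are wrong, and they differ in kind.

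The first is the label. A usual-care comparator is not a placebo. Intervention patients are shown the study videos and given a web address for them, so they can hardly be masked. The plan does not say so outright, but nothing in it would mask them. The label overstates what the trial can conclude, most of all for the self-reported scales of functional status, dyspnea, fatigue and self-efficacy.

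The second is the primary endpoint. Whether a hospitalization or ED visit happened is a matter of fact. Whether it was HF-related is a judgement, particularly in patients with several comorbidities. The only role described near that judgement is the research nurse, who belongs to the staff group that recruits patients and shows the videos. The 30-day contact also reveals the arm, because only intervention patients get the video survey. If knowledge of the arm tips borderline events one way, the primary comparison shifts and the nominal 5% error rate no longer holds.

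**Working it through.** **Inputs.** From the sample size paragraph and Analyses: control rate 28%; 33% relative decrease, so 0.28 × 0.67 = 18.76%; 329 evaluable per group; two-sided Pearson chi-square; alpha 0.05; 80% power; 10% attrition. Assumed here: the share m of intervention-arm HF events recorded as not HF-related, with none relabelled in the control arm.

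**1. The plan's own figure.** Mean rate = (0.28 + 0.1876)/2 = 0.2338.

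n = [1.96 × √(2 × 0.2338 × 0.7662) + 0.8416 × √(0.28 × 0.72 + 0.1876 × 0.8124)]² / 0.0924²
= [1.96 × 0.5986 + 0.8416 × 0.5950]² / 0.0924² = 328.2, so 329 per group.

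Then 329/0.9 = 365.6, so 366 per group and 732 in total. The plan's figures reproduce and are not in dispute.

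**2. False-positive rate under one-directional relabelling.** The true rate is 28% in both arms, and the recorded intervention rate is q = 0.28 × (1 − m). With d = 0.28 − q and p̄ = (0.28 + q)/2:

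- SE0 = √(2p̄(1 − p̄)/329)
- SE1 = √((0.28 × 0.72 + q(1 − q))/329)
- P(significant, favouring video) = Φ((d − 1.96 × SE0)/SE1)
- P(significant, favouring control) = Φ((−d − 1.96 × SE0)/SE1)

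For m = 10%: q = 0.252, d = 0.028, SE0 = 0.03445, SE1 = 0.03443. The two terms are Φ(−1.148) = 0.1255 and Φ(−2.774) = 0.0028, which sum to 0.128.

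| m (assumed) | Recorded rate | Events moved (329 × d) | Favouring video | Two-sided |
|---|---|---|---|---|
| 0% | 28.0% | 0 | 2.5% | 5.0% |
| 2% | 27.4% | 1.8 | 3.6% | 5.3% |
| 5% | 26.6% | 4.6 | 6.0% | 6.9% |
| 10% | 25.2% | 9.2 | 12.6% | 12.8% |
| 20% | 22.4% | 18.4 | 38.0% | 38.0% |

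**3. How many decisions matter.** At the planned effect the counts are about 92 (329 × 0.28) against 62 (329 × 0.1876), giving z = 2.76. If eight more intervention-arm events are counted as HF-related (92 against 70), z = 1.99. With nine (92 against 71), z = 1.90 and significance is lost.

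**4. Cost of an imperfect but even-handed definition.** Suppose a fixed definition misses the same share of true HF events in both arms (assumption). At 10% missed, the rates are 25.2% and 16.9%, and power falls from 80.1% to 74.5%. At 20% missed, they are 22.4% and 15.0%, and power is 68.2%.

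**The case against.** The strongest reply is that the endpoint is better protected than the label suggests. Its components are discrete events, looked for first in records written by clinicians who are nominally masked. Moving an event from HF-related to other leaves all-cause HCRU unchanged, and that is already a secondary outcome tested the same way. Nothing in the documents supports any particular relabelling share, or its direction. At 2% or 5% the error rate barely moves. The Design section also states openly who is masked and that this may fail.

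Most of this stands, and it limits the size of the concern. It does not remove it. Masked clinicians write the record, but the HF-related decision comes afterwards and no masked person is assigned to it. The all-cause check is partial: it cannot tell a real HF-specific effect diluted by other events from relabelling, and it does not cover events missed unevenly between arms.

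Three stronger readings are tempting, and the documents do not support them:

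- **The nurse who showed a patient the video later classifies that patient's events.** The plan shows one staff group doing both kinds of work, not one individual doing both for the same patient. It never names who classifies.
- **The primary result will be biased.** Only the opportunity is shown.
- **Masking is already available at no cost through the billing database and the coded forms.** The plan uses "billing data retrieved from Cleveland Clinic billing database" for baseline items only. It mentions no diagnosis codes or follow-up extraction, and codes would not settle deaths or events known only by telephone. That "all other baseline and follow-up data collection forms contain only research numbers" protects confidentiality; it hides no allocation from a nurse reading a patient's record.

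**Conclusion.** The concern holds as a gap in the design. The placebo-controlled label does not match the control arm; that needs no assumption. Masking covers only clinicians and unit nurses, and the HF-related decision behind the primary endpoint has neither a definition nor a masked classifier.

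The numerical consequence is conditional. With no true effect, the two-sided false-positive rate runs from 5.3% to 38.0% as the share of intervention-arm HF events relabelled goes from 2% to 20%. This assumes relabelling in one direction and one arm only, a 28% true rate in both arms and 329 evaluable per arm. The shares are illustrations, not estimates. At the planned effect, about nine classification decisions separate a significant from a non-significant result, so the point should be settled before events are classified.

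**What to change.** 1. Describe the trial as usual-care controlled, with clinicians and unit nurses nominally masked and patients and research staff not masked.
2. Before any event is classified, fix one written definition of HF-related for hospitalizations, ED visits and deaths, using recorded principal diagnoses where available. State how events known only by telephone are handled.
3. Have each event classified by an existing research nurse who did not enroll that patient or show the video. That nurse should work without the allocation and before the video survey is opened.
4. Add a sensitivity analysis of the primary endpoint limited to EMR-documented events, and read it alongside 30-day all-cause HCRU.

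**Cost.** Protocol wording, a definition, one extra analysis and a duty rota among existing staff. The plan gives no staff numbers by site, so the rota may be harder at small hospitals. The sample size stays at 329 evaluable and 366 enrolled per group. A fixed definition will misclassify some events. If the errors are equal between arms, they lower power rather than favour an arm: to about 75% if 10% of HF events are missed, so the definition should not be drawn too narrowly.

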The following outcomes will be assessed:

PRIMARY

1. 30 ± 6 days *first occurrence* of post-discharge **HF-related** HCRU; defined as hospitalization, emergency department [ED] visits, death or cardiac transplantation/ ventricular assist device [VAD] implant-- individual components and combined),

SECONDARY:

2. 90- and 180-day ± 6 days *first occurrence* of post-discharge **HF-related** HCRU; defined as hospitalization, emergency department [ED] visits, death or cardiac transplantation/ ventricular assist device [VAD] implant-- individual components and combined),
3. 30-, 90- and 180-day ± 6 days *first occurrence* of post-discharge **all-cause** HCRU; defined as hospitalization, emergency department [ED] visits, death or cardiac transplantation/ ventricular assist device [VAD] implant-- individual components and combined),
4. 30-, 90- and 180-day ± 6 days *time to* first occurrence of **all-cause** and **HF-related** post-discharge HCRU (individual components and combined),
5. 30-, 90- and 180-day ± 6 days *total all-cause* post-discharge HCRU (individual components and combined);
6. 30-, 90- and 180-day ± 6 days *total HF-related* post-discharge HCRU (individual components and combined);

NCT-03657459

7. Change in *functional status* from baseline to 30-, 90- and 180-days \pm 6 days after hospital discharge,
8. Change in *dyspnea scores* from baseline to 30-, 90- and 180-days \pm 6 days after hospital discharge,
9. Change in *fatigue scores* from baseline to 30-, 90- and 180-days \pm 6 days after hospital discharge, and
10. Change in *self-efficacy for managing symptoms* from baseline to 30-, 90- and 180-days \pm 6 days after hospital discharge
11. Differences in primary and secondary outcomes (1-10) among *intervention-group participants*, after creating 3 sub-groups based on post-discharge video viewing ([a] total number of times videos were watched, [b] viewed by caregivers/family in the hospital, and [c] viewed by caregivers/family post hospital discharge.

Specific aims and hypotheses:

1. Determine the effects (and time to effects) of HF danger signs education on *first occurrence*, *time to first occurrence* and *total* all-cause and HF-related HCRU after hospital discharge: hospitalization, ED visit, death, cardiac transplantation or VAD.
2. Examine if functional status, dyspnea, fatigue and self-efficacy for managing symptoms scores change over time and the direction of change.

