- At 30-day follow-up, there are 2 options to collect data on 4 tools with 40 items in total, that will take ~ 10 minutes or less to complete (usual care group) or 5 tools with 43 items in total, that will take ~ 10 minutes to complete (intervention group) and include functional status, dyspnea, fatigue self-efficacy, and a 3-item video viewing experience survey for the intervention group, by telephone or mail. As a secondary method, patients who are hospitalized during the follow-up period may receive tools in person by a research nurse.

Limitations and Anticipated Problems

Patients and caregivers may never view the Wellflix, Inc. HF danger sign videos after discharge, and/or forget content viewed during hospitalization. Patients may view/hear, but ignore, message content. Patients may drop out before the 180-day follow-up data collection. Analyses will be completed using “intent to treat” methods. In this way, we will be able to learn the effect size of the intervention among all patients randomized to the intervention group.

No adverse effects are anticipated, as the intervention in this research are HF danger signs videos that cannot create harm to patients. Video scripts provide messages that may be available in commercially available videos and or written materials used in usual HF care education and discharge instruction materials. There are no risks of adverse events from the intervention itself.

Human Subjects Protection

Approval by the Cleveland Clinic Institutional Review Board will be sought prior to study initiation. We believe this study is minimal risk as the intervention is composed of back-to-back video viewing of 3 HF danger signs (fatigue, dyspnea and edema). Video self-care messages delivered through demonstration, imitation and modeling are part of usual heart failure post-discharge care, but are delivered using principles of Bandura’s social learning theory, to enhance ability to complete independently after viewing videos.

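### The only scheduled collection of in-hospital family viewing is the 30-day survey, so video-arm patients who die or do not respond before it may have no value for that factor

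*Combined protocol and SAP*

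**What the plan says.** - **Use of the factor.** Study Purposes, outcome 11, compares outcomes 1 to 10 within the intervention group by three viewing factors. The second is "b] viewed by caregivers/family in the hospital". Outcomes 1 to 6 are HCRU outcomes, and death is one of the HCRU components. Hypotheses 3a to 3c rest on the viewing factors.
- **Instrument.** Outcomes and Measurement heads its paragraph "Video Watching Experiences in-hospital and at 30 day follow-up (intervention group only") and continues: "A 3-item, investigator-developed survey will assess video watching characteristics". The three items are total viewings, family viewing in hospital, and family viewing after discharge up to 30 days.
- **Schedule.** Data Collection lists the tools to be "completed at 30 ± 6 days: functional status, dyspnea, fatigue, self-efficacy for managing symptom and video watching experiences". It adds: "The intervention-only group survey on video watching experiences will be administered last". Feasibility repeats the day-30 arrangement: "a 3-item video viewing experience survey for the intervention group, by telephone or mail". It allows in-person completion for patients who are back in hospital during follow-up.
- **Delivery.** The Intervention section states: "During hospitalization, videos will be loaded into an iPAD and will be viewed through the iPAD". Data Collection has research personnel give this education after randomization. Neither section mentions recording who else watched.
- **Analysis.** The Analyses section stratifies the video group by viewership and applies similar methods to the same outcomes. It has no rule for patients whose viewership is unknown. Limitations and Anticipated Problems says only that analyses follow intent-to-treat methods.

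**The concern.** Total viewings and post-discharge family viewing cannot be known when the patient leaves hospital. In-hospital family viewing can be, and study staff are in the room when the video is shown. Asking about it a month later makes a pre-discharge fact available only for patients who are alive, reachable and willing to answer, and makes it depend on memory.

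The outcome compared across this factor includes death. A patient who dies before the survey has an all-cause HCRU event and no value for the factor. Whether the factor is missing then depends partly on the outcome, and the viewership comparison is made in a group selected by that outcome. The same selection carries into the 90- and 180-day comparisons by this factor.

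**Working it through.** **1. Is the item part of the day-30 contact?** Items per scale (Outcomes and Measurement): functional status 12, dyspnea 10, fatigue 10, self-efficacy 8.

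- Usual care: 12 + 10 + 10 + 8 = 40, as the plan states.
- Intervention: 40 + 3 = 43, as the plan states.

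So all three viewing items, including the in-hospital one, are asked at 30 ± 6 days.

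**2. Is it also collected in hospital?**

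- The Outcomes and Measurement heading can be read as two collection times, because the heading before it names baseline as a collection time. It can also be read as the two viewing periods the survey covers. The full survey could not be completed in hospital, since one item concerns the period after discharge.
- Data Collection and Feasibility schedule the survey at day 30 and nowhere else.
- The baseline battery ("all 6 tools have only 71 items (in total")) does not include it. This settles nothing: baseline forms are completed before randomization, so before any viewing.

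Day 30 is therefore the only scheduled collection. An in-hospital collection is hinted at in one heading and carried out by no procedure.

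**3. What follows if day 30 is the sole source?** A stratified comparison needs a stratum for each patient. HCRU comes from medical records or telephone, so the outcome may be known while the factor is not. Intent to treat fixes the randomized group; it does not supply a viewership level.

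**4. How many patients?** The video arm has 366 patients: 329 / 0.90 = 365.6, rounded up. The documents give no 30-day death rate, so take 1% to 5% dying before the survey as an assumption.

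- 366 × 0.01 = 3.7, about 4 patients.
- 366 × 0.05 = 18.3, about 18 patients.

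Survivor non-response is not given either. With an assumed 20% on top of 5% deaths, the number is 18.3 + 0.20 × (366 − 18.3) = 87.8, about 88 patients.

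**5. What does this do to the event rate among classified patients?** The design rate in the video arm is 28% − 9.2% = 18.8%, or 366 × 0.188 = 68.8 events. Suppose every assumed death counts as such an event and all survivors respond.

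- 1% deaths: (68.8 − 3.7) / (366 − 3.7) = 65.1 / 362.3 = 18.0%.
- 5% deaths: (68.8 − 18.3) / (366 − 18.3) = 50.5 / 347.7 = 14.5%.

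This is a shift in the overall rate of the classified group. It is not a bias in the difference between patients whose family watched and those whose family did not. That would need the split on the factor and the distribution of deaths and non-response across it, and the documents give neither.

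**The case against.** The strongest reply is that the heading in Outcomes and Measurement names the hospital as well as day 30, so the item may be meant to be collected at both times. The 43-item count shows that it is asked at day 30, not that it was never asked before. This stands as far as it goes: the documents do not support saying flatly that day 30 is the sole source. But the reading has no procedure behind it, and if it is the intended one, the plan must still say which answer defines the factor.

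A reader might go further and infer the following, none of which the documents support:

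- **That every patient who dies or does not answer is excluded.** No exclusion rule is stated. HCRU is still captured from records, and rehospitalized patients may be surveyed in person. With a window of ± 6 days, a patient surveyed on day 24 who dies by day 30 is classified and counted. The in-person route does not help patients who have died, and it makes ascertainment depend on rehospitalization, itself an HCRU event.
- **That about 37 patients (366 × 0.10 = 36.6) will lack the survey.** The 10% is the sample-size allowance for loss to follow-up on the HCRU endpoint, not a survey non-response rate.
- **That the loss removes a known share of HF-related events.** This needs an assumed death rate and every death to count as HF-related.
- **That the plan concedes poor memory.** Feasibility speaks conditionally of forgetful patients, and the inclusion criteria require intact cognition. Recall over a month is a weakness without that.

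It is also fair to say that family presence is self-selected, so the comparison stays associational however well the factor is recorded.

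**Conclusion.** The point holds in limited form. The only scheduled collection of in-hospital family viewing is the survey at 30 ± 6 days, and the heading that suggests otherwise is not matched by any procedure. If day 30 is the sole source, the factor is missing for patients who die or do not respond before the survey. The missingness then depends partly on the outcome, and the Analyses section does not say how to handle it.

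Under an assumed 1% to 5% mortality before the survey, about 4 to 18 of 366 patients would be unclassified through death alone. The size and direction of bias in the comparison between strata cannot be derived from the documents. The comparison is secondary, non-randomized and confined to the video arm; the primary analysis and the sample size are unaffected. The change is still worth making, because it costs little and removes a dependence on the outcome that need not exist.

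**What to change.** - Have the research personnel who show the video record on the case report form, at the in-hospital session, whether a family member or caregiver watched (yes/no).
- Define factor [b] of outcome 11 from that record for all video-arm patients shown the video.
- Keep the 30-day survey for total and post-discharge viewing, with its in-hospital item as a supplement.
- Align Outcomes and Measurement, Data Collection and Feasibility on when each viewing item is collected, and state in Analyses how missing viewership is handled.

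The cost is one tick box and a few sentences of protocol text, with no extra staff because the session already takes place. One small downside remains: family viewing in hospital after the nurse has left would be captured only by the supplementary survey item.
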